1.7. Data Analysis

Overview. Initially we will assess whether our stratified randomization procedures yielded groups equivalent in groups on the stratification factors and other demographic and clinical variables. These analyses will be completed with chi-square statistics for categorical variables (or Fisher Exact statistics as needed for small ns) and t-tests for continuous measures (or Kruskal-Wallace tests if there are serious deviations from normality on these variables). Our initial analyses of the primary dependent measures for Veterans, the SAPS and SANS, and for family members/supporters, Caregiver Burden, will test the mean ratios at time points 12 and 15 months to test for non-inferiority. Then the analyses will be move to mixed effect regressions with the primary effects of interest the interaction between time of measurement and treatment group. The use of mixed effect regression allows us to include subjects with partially complete data, e.g. missing the 6 month interview but have baseline, and 12 month interview data available (see below). Prior to the regression analyses we will also check to insure that the continuous measures (SAPS, SANS, Caregiver Burden) are normally distributed. If these assumptions are violated we will identify appropriate transformations to normalize these outcomes or use different forms of the outcome variables and regression techniques that do not require normality to be appropriate. Also of interest will be differences between completers vs. non-completers across the 2 groups as well as within groups (see specifics below under Aims 1 and 2).

1.7.1. Specific Aim 1

We will conduct a 2-arm, non-inferiority randomized comparative effectiveness trial of DSW and in-person multi-family MFG. We will compare changes in severity of Veterans' of psychiatric symptoms (i.e., positive and negative symptoms), and caregiver psychological burden, during the treatment period and then 3-months post-treatment.

Hypothesis 1.1. Veterans participating in DSW will do as well or better than those participating in in person MFG with an equivalence ratio of 1.20-1.47 (depending on the coefficients of variance of the measures assessed) at time points 12 and 15 months.

Hypothesis 1.2. Family caregivers participating in DSW will do as well as or better than those participating in in-person MFG with an equivalence ratio of 1.17-1.29 (depending the coefficient of variance of the measure assessed) at time points 12 and 15 months.

Hypotheses 1.3. When compared to in-person MFG, Veterans and family members receiving DSW will have higher treatment initiation, engagement, attendance, lower drop-out, and higher perceived social support.

1.7.2. Specific Aim 2

We will conduct exploratory analyses to identify Veteran and family characteristics that are associated with severity of psychiatric symptoms and caregiver burden across both treatment arms. Analyses will look for important moderators (e.g. baseline symptom level, distance from hospital, age, technology expertise) as well as mediators (e.g., in-person meeting attendance, amount of DSW usage).

These analyses will be completed by supplementing the mixed effect regressions with demographic (age, race education), pre-study computer experience, support (living situation) and clinical characteristics (symptom severity, severity of cognitive impairment) of subjects that affect the relationships between the treatment and outcomes. Analyses will be carried out across both arms and then for each arm separately. While it is possible to test the treatment X non-treatment moderators with interaction terms the number of subjects precludes analyses that include all factors and interactions.

Mediating effects of the different intervention components and different patterns of attendance and engagement are likely to occur in this study and will also be identified with mixed effect regressions. To test for mediating effects we will compare the relationships between treatment and outcomes and these potential mediating variables and outcomes. We assume that exposure, i.e., increased numbers of in-person session attendance, or more usage of DSW, will lead to greater improvements. These will help us to identify whether it is the amount of time spent on the materials/in treatment, or the duration of time one is exposed to treatment. Those in DSW and in-person MFG could have up to 1 year exposure, but usage patterns will identify the actual period of time over which Veterans were actually exposed to MFG materials, and the amount of time they used those materials. Thus, though the duration is the same in both treatments, the actual amount of exposure is not necessarily the same in both. For these analyses with 80 subjects in a multivariable regression with treatment included the detectable R^2 difference of an additional variable is 0.06 with 3 added variables it is 0.09 and with as many as 8 additional variables (or degrees of freedom) the detectable difference in R^2 is 0.12 (alpha=0.05, power=80%). The usual rule of thumb is to include at most $n/(8-10)$ variables in a multivariable regression, thus the analyses will be limited to 8 variables including the treatment variable.

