1.0. Research Study methods

This project will conduct a randomized comparative effectiveness clinical trial with 89 Veterans with schizophrenia or schizoaffective disorder (SZ/SZA). In addition family members or other informal support persons will be invited to formally join the study with each Veteran with SZ/SZA who consents to join the study. These subjects will be randomized into one of two study arms: 1) the Daily Support Website (DSW), this group will receive access to the DSW intervention that includes three facilitated group forums, Ask Our Experts Your Questions, the Questions and Answers Library of previously asked and answered questions, educational materials, tutorials and self-help guides, libraries, and community resources lists; and 2) in-person Multi-Family Group (MFG). This is the standard in-person method for providing multi-family psycho-education to veterans with schizophrenia and their supporters (e.g., family members) in the VA. This group will receive the standard and manualized MFG treatment provided by the VA, it will be provided by trained clinicians, and supervised by those who provide supervision in the VA. In both study arms, participants will receive all treatment as usual (TAU). In the DSWDSWDSW arm, as needed Veterans can receive a new or refurbished computer and Internet access at home.

All Investigators and staff on the research team will have completed educational training required by the VA.

Recruitment

Veterans will be recruited from the two VA campuses in the Pittsburgh area, University Drive, and H.J.Heinz, and five Community Based Outpatient Clinics (CBOCs). Veterans will be randomly assigned to the two treatment arms, and will be stratify by: distance from/difficulty traveling to the VA medical center (<40 min. or do not have significant transportation barriers, vs. ≥ 40 min. or have significant transportation barriers); number of prior psychiatric hospitalizations (<5 vs. ≥ 5); and gender. The study statistician will generate randomization tables prior to beginning recruitment, and these will be used to assign participants to one of the arms. Flyers describing the study will be available at each site.

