A standard question will be asked of the Veteran to identify the person who is their primary family supporter or other primary support person. To verify this, a similar question will be asked of the support person identified. If there is a tie between two or more support persons (e.g., family members), it will be the person who spends the most face-to-face time with the Veteran who will be used as the “primary” support person for data collection.

Recruitment of Family/Support persons

To recruit family members and support persons, the Veteran will be asked to identify appropriate persons (family, other support persons). A brochure explaining the study will be sent to such persons, either by mail or the Veteran will provide it to him or her. Staff will also tell family about the study when they see them at a clinic, or talk with them as part of standard clinical care over the telephone. Family and support persons will be provided with a number and contact information of a study recruited, who they can get in touch with for additional information concerning the study. If they are interested in participating they will be formally consented to join the study by research staff. The primary support person/family member for the veteran must be ≥ 18 years old and able to speak and read English at the 5th grade level.

1. After consenting, and then baseline data collection, participants will be assigned to one of two treatment arms. Those in each arm will receive a different form of multi-family psychoeducation treatment. One arm will receive Multi-

Family Group (MFG). This treatment is provided in in-person group meetings that occur every other week for one year. The other arm will receive the treatment for one year via the Daily Support Website.

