b. Daily Support Website (DSW). Participants assigned to be in the Daily Support Website arm will receive access to this website and its associated functionalities. The DSW provides the following five resources. (1) Three on-line group forums. One for persons with SZ/SZA only (the SZ/SZA peer group), one for family/supporters only, and a combined group for both persons with SZ/SZA and support persons. In each group the therapists emphasized discussions that focus on problem-solving, alleviating stresses, and encouraging peer interactions. (2) Educational materials and tutorials. (3) A section to ask questions and receive an answer from the therapists associated with the project. (4) A library of previously asked and answered questions. (5) A list of community resources. Those who do not have a computer will have a computer (e.g., laptop, touch pad, or chrome book) provided to them, and Internet service, both free of charge to allow them to participate in the intervention. After their participation is over they will return the equipment.

The DSW treatment begins with two participant engagement activities. The first activity is joining sessions where the study therapist(s) meets with each individual participant (veteran, and when present supporter). These meetings can be in-person, via phone or over the internet. The purposes of the meetings are to develop a collaborative relationship, discuss the DSW, facilitate comfort with the e-health approach to receiving treatment, and develop an individual goal or identify a current 'issue' or 'complaint' that is bothering the individual. These meetings can involve both individual participant meetings as well as joint family meetings (i.e., veteran and his/her family/supporters). The number of meetings varies by

individual and family need (as jointly determined by the therapist and the participants). During the initial treatment period a therapist or research staff member may call a participant to ensure there are no issues with accessing the DSW, such as problems with equipment or lack of understanding of one or more aspects of using the DSW.

2. Participant Data collection. Outcomes data will be collected at scheduled time points of baseline (0), 6, 12, and 15 months. Each of these sessions is estimated to take about 2 hours. The data to be collected is described in Table 4.1.

Table 1.1. Data collection

Information	Measure

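### The 12- and 15-month margin test names no baseline or stratification term, and the mixed model that does use baseline carries no margin: an inexpensive gain in precision is left unused

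*Combined protocol and SAP*

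**What the plan says.** All references are to the combined protocol and SAP.

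- **Margin test.** Section 1.7 (Overview) states that the initial analyses of SAPS, SANS and caregiver burden "will test the mean ratios at time points 12 and 15 months to test for non-inferiority". Section 1.8 defines the ratio as the DSW mean over the MFG mean, with a margin of 1.2 for symptoms and 1.17 for burden. No covariate is named.
- **Mixed model.** The Overview then moves to "mixed effect regressions with the primary effects of interest the interaction between time of measurement and treatment group". It gives as a reason that "The use of mixed effect regression allows us to include subjects with partially complete data", with baseline among the repeated measurements. No margin, confidence limit or decision rule is attached.
- **Scale.** If normality fails before the regressions, "we will identify appropriate transformations to normalize these outcomes", or other outcome forms and methods are used.
- **Baseline.** Section 1.0, item 1: "After consenting, and then baseline data collection, participants will be assigned to one of two treatment arms". Item 2: "Outcomes data will be collected at scheduled time points of baseline (0), 6, 12, and 15 months".
- **Strata.** Under Recruitment in section 1.0, Veterans "will be stratify by: distance from/difficulty traveling to the VA medical center", and also by number of prior psychiatric hospitalisations and by gender. In the Overview these factors return only in a check of group balance.
- **Exploratory use.** In section 1.7.2 (Aim 2): "Analyses will look for important moderators (e.g. baseline symptom level, distance from hospital, age, technology expertise". No margin applies there.

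**The concern.** The plan splits two things that belong together. The step that can answer the non-inferiority question names no use of baseline or of partial follow-up. The step that uses both asks a different question: a non-significant time-by-treatment interaction does not show that DSW is no more than 20% worse.

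Baseline scores are taken before assignment and the strata are part of the randomisation, so all of them can properly enter the deciding test. If baseline predicts the later score, leaving it out widens the interval around the ratio, and a DSW programme that truly matches MFG is less likely to show it. Section 1.7.1 also frames Aim 1 as a comparison of changes, while the margin test uses follow-up means alone. Leaving the choice of covariates, model and scale open until data are seen would also weaken a non-inferiority claim.

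**Working it through.** **Inputs from section 1.8.** Margin R = 1.20 (burden 1.17); CV 0.3 to 0.5; one-sided alpha 0.025; 42 per arm for power above 80%; completer targets 42 DSW and 47 MFG; enrolment 47 DSW and 70 MFG. True ratio taken as 1.

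**Assumed.** Baseline-to-follow-up correlation ρ = 0.3, 0.5, 0.7; the documents give none.

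**Formulas (log scale).** σ = √ln(1 + CV²). SE = σ·√(1 − ρ²)·√(1/n₁ + 1/n₂). Power is from the noncentral t with noncentrality ln(R)/SE and n₁ + n₂ − 2 degrees of freedom, one fewer when baseline is fitted.

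**Step 1: the plan's own figure.** CV 0.3 gives σ = √ln(1.09) = 0.2936. With 42 per arm, SE = 0.2936 × √(2/42) = 0.0641, noncentrality = 0.1823/0.0641 = 2.85 and power = 80.3%. At 41 per arm it is 79.3%. So 42 is the smallest number that reaches 80%, and it reproduces with no baseline or stratum term. The sizing matches an unadjusted test.

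**Step 2: the plan's completers.** With 42 and 47, unadjusted SE = 0.2936 × √(1/42 + 1/47) = 0.0623, noncentrality 2.93, power 82.4%. At ρ = 0.5 the SE is 0.0623 × √0.75 = 0.0540, noncentrality 3.38, power 91.6%.

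| Case | Unadjusted | ρ 0.3 | ρ 0.5 | ρ 0.7 |
|---|---|---|---|---|
| 42/47, CV 0.3, margin 1.20 | 82% | 86% | 92% | 98% |
| Same, MFG variance × 1.06 | 81% | 85% | 91% | 98% |
| Burden, 42/42, CV assumed 0.3, margin 1.17 | 68% | 72% | 80% | 92% |
| 42/42, CV 0.5, bound 1.29 | 69% | 73% | 80% | 93% |
| 47/70, all followed, CV 0.3, margin 1.20 | 90% | 93% | 96% | 99.6% |

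The 1.06 is the middle of 1 + (6 − 1)(0.01) = 1.05 and 1 + (8 − 1)(0.01) = 1.07, from the plan's dependency of 0.01 and groups of 6 to 8.

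**Step 3: partial follow-up.** A simulation enrolled 47 and 70 and lost 10% and 33% at random, half after baseline and half after month 6 (assumed). Power was 81 to 83% unadjusted, and about 86, 92 and 98% from a four-visit model with arm means constrained equal at baseline (simulation error about 1 point).

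**Step 4: the downside.** With ρ = 0 and three balanced strata unrelated to outcome, simulated power at 42/42 fell from 80.2% to 79.5%. In the four-visit model with approximate degrees of freedom, one-sided error at the margin was 2.6 to 2.9% at ρ = 0.5, against a nominal 2.5%.

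**The case against.** The strongest reply is that this is silence, not error. The Overview names no covariates but does not exclude them, and the unadjusted ratio test is valid and agrees with the sample size. That stands, so the point is an improvement and not a defect in validity.

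The size of the gain also rests on a correlation that is not in the documents. At 0.3 it is only 3 to 4 points, and if all 117 enrolled are followed, power is already about 90%. That stands too.

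For the strata, no gain has been shown: the check made them unrelated to outcome and so establishes only that including them costs little. The case for them is consistency with the randomisation.

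Finally, a log-scale model estimates a ratio of geometric means. This equals the ratio of means in section 1.8 only under conditions such as lognormal scores with equal CVs. The fix must deal with that.

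A reader might infer more than the documents support:
- *That the planned test is biased.* It is not; randomisation protects it on average.
- *That the plan ignores baseline.* It does not; baseline is a repeated measurement in the mixed model.
- *That MFG group nesting belongs to this loss of precision.* Section 1.8 says a correction is needed and no analysis names one, but that is a separate, small consistency point. Ignoring nesting at a dependency of 0.01 gives an error of 2.6 to 2.7%, and accounting for it costs power.

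**Conclusion.** The point holds as a low-cost improvement. The only analysis with a margin leaves out information the trial already collects, and the model that uses that information is aimed at a quantity that cannot deliver the conclusion.

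For symptoms, the expected gain runs from about 3 points (ρ 0.3) to about 16 points (ρ 0.7) at the plan's completer numbers. For caregiver burden at 1.17 the gain is larger, about 4 to 25 points, from a start of 68%. These figures assume the log scale, a true ratio of 1, CV 0.3 (for burden this CV is itself an assumption) and the stated range of correlations. They do not show that the trial is underpowered for symptoms at 1.20, nor how much would be gained in practice.

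**What to change.** In section 1.7 (Overview), make the planned mixed model carry the margin test:

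1. Estimate the DSW/MFG ratio at 12 and at 15 months from that model, each with its one-sided 97.5% upper limit.
2. Use baseline either as a repeated outcome with arm means constrained equal at baseline, or as a covariate. In the covariate form, state that people with no follow-up score do not contribute without imputation.
3. Include the three stratification factors and use small-sample degrees of freedom.
4. Compare each upper limit with one margin per outcome, fixed in advance. Sections 1.8 and 1.7.1 must first be reconciled: they give 1.2 and 1.17 in one place, and 1.20-1.47 and 1.17-1.29 in the other.
5. Fix the scale in advance. Either estimate the ratio of means as section 1.8 defines it, or state that a log-scale model gives a geometric-mean ratio and give a rule for zero scores if they can occur. Make the transformation provision agree with that choice.

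The cost is SAP wording and modest programming, with no new data or visits. Power falls by under 1 point if baseline and strata prove uninformative. The complete model has not been simulated as one piece, so its error rate at the margin should be checked before the SAP is final, given the 2.6 to 2.9% seen with approximate degrees of freedom. How to handle MFG nesting should be decided separately.

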1.8. Power, Sample Size, with Estimation of Missing Subjects Follow-up

The primary Veteran outcomes are SAPS and SANS, and family outcome is caregiver burden. Note, for these outcome measures higher scores indicate worse symptoms. The equivalence ratio that will be tested is the mean of DSW/mean of in-person MFG. For both Veterans and family members we plan for the study to detect equivalence ratios of 1.2 for the two measures of psychotic symptoms (SAPS and SANS) and caregiver burden. In these hypotheses tests the null hypotheses are that DSW outcome means are inferior to MFG. The ‘alternative’ hypotheses are that outcomes means in the DSW arm are equivalent to outcomes in the in-person MFG arm. If as an example, the symptoms are higher in the DSW arm, and thus the ratio of the mean of the DSW arm to the mean of the in-person MFG arm exceeds 1.2 (i.e. mean of DSW > mean in-person MFG by 20% or more) we will accept the null hypothesis that the mean of DSW > mean of in-person MFG, and that DSW is not as effective as in-person MFG. Any ratio of DSW/MFG that is < 1.2 will cause us to reject the null hypothesis and accept the alternative that they are equivalent. For the caregiver burden scale the equivalence ratio that leads to rejection is slightly smaller, it is 1.17 because there is only 1 primary measure. With 42 subjects per treatment arm, power is >80% with one tailed alpha =0.025 to detect equivalence ratios of 1.2 (and above). For testing whether DSW is superior to in-person MFG on the illness symptom measures we can reverse the ratio and test whether (mean of in-person MFG/mean DSW) is > 1.20. For these sample size calculation we used reported data to estimate the coefficients of variation (CV) of the scales. CVs commonly range from 0.3-0.5 and within this range there were differences in the calculated equivalence ratios. For alpha =0.025, and CV equal to 0.3 the equivalence ratio bound was 1.20 with an increase to 1.29 for a CV of 0.5.

For the in-person MFG arm a correction for nesting of subjects in a group is needed, which increases the number of subjects required. If it is assumed that this dependency is 0.01 and groups are of size 6-8 then variance inflation factor is on the order of 10%, resulting in 46-47 subjects being needed for the in-person MFG arm. Because DSW is available separately for each Veteran and family member it is not necessary to increase the 42 subjects needed for this group. The

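### Section 1.8 enlarges the MFG arm for nesting in therapy groups, but the primary analyses in section 1.7 state no group term, so a test that ignores group is mildly anti-conservative

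*Combined protocol and SAP*

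**What the plan says.** On sample size, section 1.8 is explicit: "For the in-person MFG arm a correction for nesting of subjects in a group is needed, which increases the number of subjects required". It continues: "If it is assumed that this dependency is 0.01 and groups are of size 6-8 then variance inflation factor is on the order of 10" per cent, "resulting in 46-47 subjects being needed for the in-person MFG arm". For DSW, it says that "it is not necessary to increase the 42 subjects needed for this group". The test is one-sided at 0.025 against a ratio of 1.2.

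On analysis, the section 1.7 Overview gives two steps for SAPS, SANS and caregiver burden. The first "will test the mean ratios at time points 12 and 15 months to test for non-inferiority". The second is "mixed effect regressions with the primary effects of interest the interaction between time of measurement and treatment group". The reason given for the mixed model is that people with a missed visit can still contribute. Its random effects are not listed. Sections 1.7.1 and 1.7.2 add hypotheses, covariates, moderators and mediators, but mention neither therapy group, clustering nor an ICC.

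**The concern.** The plan recognises the dependency when it counts participants and does not mention it again when it describes the tests. These are separate tasks. Adding MFG participants offsets the power lost to nesting. It does nothing to a standard error that treats those participants as independent.

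Some dependency is to be expected. As the MFG arm is described, members of a group share a workshop tailored to them, then meet every other week with the same two clinicians and work through one member's problem together. Supporters attend the same groups, so caregiver burden is exposed as well.

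The direction matters. A positive ICC left out of the analysis understates the variance of the MFG mean. In a non-inferiority comparison this makes it easier to conclude that DSW is as good as MFG, so the one-sided error exceeds the stated 0.025.

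**Working it through.** **Inputs.** From section 1.8: 42 DSW and 47 MFG completers; 70 MFG Veterans enrolled; one-sided alpha 0.025; ratio margin 1.2; CV 0.3; ICC 0.01; groups of 6-8; inflation of about 10%. Assumed here: ICCs of 0.05 and 0.10, to show sensitivity; equal total variance in the two arms; DSW un-nested, as the plan has it.

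**The plan's own figures.** On the log scale, SD = √ln(1 + 0.3²) = 0.2936 and the margin is ln 1.2 = 0.1823. Then n = 2 × (1.96 + 0.842)² × 0.2936² / 0.1823², which rounds up to 41 per arm. With the t distribution, 42 per arm has 80.3% power, so 42 reproduces. Next, 42 × 1.10 = 46.2, which rounds up to 47, so 46-47 reproduces from the stated 10%. The usual formula, VIF = 1 + (m − 1) × ICC, gives 1.05 for m = 6 and 1.07 for m = 8, that is 44.1 to 44.9, or 45 participants. The plan's 10% is therefore slightly generous for its ICC.

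**Effect of ignoring group.**
- Naive variance factor: 1/42 + 1/47 = 0.04509.
- True variance factor: 1/42 + VIF/47.
- SE ratio = √(true / naive).
- True one-sided alpha = 1 − Φ(1.96 / SE ratio).

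Example with VIF 1.07: 0.02381 + 0.02277 = 0.04658; the SE ratio is √(0.04658 / 0.04509) = 1.016; 1.96 / 1.016 = 1.93; alpha = 0.0269.

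| ICC | Analysed per group | VIF | SE ratio | True one-sided alpha |
|---|---|---|---|---|
| 0.01 (plan) | 6 | 1.05 | 1.012 | 0.0264 |
| 0.01 (plan) | 8 | 1.07 | 1.016 | 0.0269 |
| plan's stated 10% | – | 1.10 | 1.023 | 0.0277 |
| 0.05 (assumed) | 6 | 1.25 | 1.057 | 0.0319 |
| 0.05 (assumed) | 8 | 1.35 | 1.079 | 0.0347 |
| 0.10 (assumed) | 6 | 1.50 | 1.112 | 0.0390 |
| 0.10 (assumed) | 8 | 1.70 | 1.153 | 0.0446 |

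A simulation of an unadjusted two-sample t-test at the margin (100,000 runs per setting) agrees. For m = 6 and m = 8 it gives 0.0263 and 0.0270 at ICC 0.01, 0.0319 and 0.0340 at 0.05, and 0.0374 and 0.0438 at 0.10.

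**If attrition thins the groups.** Suppose 70 Veterans form 10 groups of 7 and 47 are analysed, an average of 4.7 per group. Then VIF = 1 + 3.7 × ICC, and alpha is 0.0260, 0.0301 and 0.0353 at ICC 0.01, 0.05 and 0.10.

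**Number of groups.** 47/7 = 6.7 and 70/6 = 11.7, so roughly 7 to 12 groups, depending on whether completers or enrolled Veterans are counted.

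**The case against.** The strongest reply is that the plan is silent rather than wrong. The mean-ratio test comes with no variance formula, and the mixed model lists no random effects at all, not even one for subject. A group effect is therefore unstated, not ruled out. This stands. A reader might infer that the plan commits itself to an independence analysis, and the text does not go that far. But silence leaves the choice open until the data are in, and an analyst following only the written description would have no reason to include group.

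A reader might also infer that the plan's confidence limits are too narrow. The documents do not support that wording, because no confidence limit for the ratio is defined. The rule in section 1.8 compares the ratio itself with 1.2. What can be said is that a standard error ignoring group is too small for a test at the stated one-sided 0.025.

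Third, the effect at the plan's own ICC is small, and the larger error rates rest on ICCs that the documents do not contain. That also stands and limits the weight of the point. Against it, the 0.01 is itself introduced as an assumption, with no source given.

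Finally, with so few groups the ICC will be poorly estimated and a small one may often come out at zero, so a random intercept may change little in a given dataset. This is a fair caution about the remedy. It does not justify leaving the method unstated.

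**Conclusion.** The point holds as an omission of modest size. Section 1.8 says a nesting correction is needed, and section 1.7 carries it into neither primary analysis. If group is ignored, the true one-sided alpha is about 0.026-0.027 at the plan's ICC, or 0.028 with its stated 10% inflation, instead of 0.025. It reaches 0.032-0.045 only at ICCs of 0.05-0.10, which are assumed here, and less if the analysed groups are smaller than 6-8.

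The documents do not support a claim of serious error inflation under the plan's own assumptions. The figures assume 42 and 47 analysed Veterans and equal total variance in the arms. The argument applies to caregiver burden in the same direction, but no figure is given because the plan does not state how many supporters will be analysed.

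**What to change.** State in section 1.7 how MFG group enters both the 12- and 15-month non-inferiority test and the mixed regressions. One suitable form is a partially nested model with a random intercept for group in the MFG arm only. DSW participants, and MFG participants who never join a group, enter as singletons. Use small-sample degrees of freedom such as Satterthwaite or Kenward-Roger. Apply the same model to caregiver burden, and report the estimated ICC with its uncertainty.

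Record each participant's group explicitly. Section 1.2.11 logs session attendance but does not mention a group identifier.

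The cost is some SAP wording, one data field and one model term, with slightly wider intervals and slightly lower power. By normal approximation at CV 0.3 with 42 and 47 completers, power is about 83% with no nesting (0.1823 / (0.2936 × √0.04509) − 1.96 = 0.965). With the correct standard error it is 82.1-82.4% at ICC 0.01, and 71.8-74.9% at an assumed 0.10. Small-sample degrees of freedom would lower these a little further. With roughly 7 to 12 groups the ICC will be imprecise, so the model should be fixed in advance and not chosen on the estimated ICC.

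### Non-inferiority is tested at both 12 and 15 months with no primary time or success rule, while the stated alpha and power hold for a single test; if both times must pass, power is about 69-75%, not above 80%

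*Combined protocol and SAP*

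**What the plan says.** Section 1.8 defines the outcomes and the comparison: "The primary Veteran outcomes are SAPS and SANS, and family outcome is caregiver burden", and "The equivalence ratio that will be tested is the mean of DSW/mean of in-person MFG". It then gives the operating characteristics: "power is >80% with one tailed alpha =0.025 to detect equivalence ratios of 1.2 (and above"), with 42 subjects per arm. The bound depends on the coefficient of variation (CV), taken as 0.3 to 0.5. The section mentions no time point.

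The only allowance for multiple testing concerns the number of measures. For caregiver burden the bound is smaller: "it is 1.17 because there is only 1 primary measure".

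Section 1.7 (Overview) says the initial analyses of these three measures "will test the mean ratios at time points 12 and 15 months to test for non-inferiority". Under Specific Aim 1 (1.7.1), Hypotheses 1.1 and 1.2 each name 12 and 15 months. Neither time is called primary. Nothing says whether success is needed at both times or at one, in what order the times are tested, or how alpha is shared between them. Mixed-effect regressions follow the ratio tests, but they supply no rule for combining the two times.

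**The concern.** Each primary measure is tested twice, but the sample size supports one test per measure. Two tests can be combined in different ways, and each way changes either the chance of a false claim or the chance of a true one. Until the rule is fixed, the stated alpha and power cannot be attached to the primary conclusion.

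The two times also answer different questions. Treatment lasts one year, so month 12 measures the end-of-treatment result and month 15 measures how well it lasts three months later. If they disagree, the plan does not say what is concluded, and the choice could be made after the data are seen. In a non-inferiority trial, a false success means accepting an inferior treatment as adequate.

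**Working it through.** **Inputs from Section 1.8.** 42 per arm, one-sided alpha 0.025, margin 1.2, CV 0.3 (the low end of the stated range).

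**Assumed, because the documents give no figure.** True ratio 1.0; correlation ρ between the 12- and 15-month results 0.5-0.9; correlation between SAPS and SANS 0.2-0.4.

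**Step 1: reproduce the plan's figure.** On the log scale, σ = √ln(1 + CV²) = √ln(1.09) = 0.2936, and the margin is ln 1.2 = 0.1823. The standard error is 0.2936 × √(2/42) = 0.0641, so the noncentrality is 0.1823 / 0.0641 = 2.846. With 82 degrees of freedom the critical t is 1.989, and the noncentral t gives power 80.3%. The stated 42 per arm is therefore one test of one measure at one time, with almost no reserve. The 47 in the MFG arm only offset clustering.

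**Step 2: see what the bounds allow for.** At 42 per arm, the margin giving 80% power is:

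| One-sided alpha | CV 0.3 | CV 0.5 |
|---|---|---|
| 0.025 | 1.199 | 1.339 |
| 0.05 | 1.174 | 1.295 |

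The 1.20 for SAPS and SANS fits alpha 0.025, and the 1.17 for caregiver burden fits alpha 0.05. This suggests 0.05 split over two Veteran measures and left whole for the single family measure. That is an inference; the plan does not state it. Nothing is set aside for a second time. (Separately, Section 1.8 says "For alpha =0.025, and CV equal to 0.3 the equivalence ratio bound was 1.20 with an increase to 1.29 for a CV of 0.5". The 1.29 does not reproduce at 0.025; it fits 0.05.)

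**Step 3: both times required.** Error per measure cannot exceed 0.025, because both tests must reject. With Φ₂ the bivariate normal distribution function, power is Φ₂(b, b; ρ), where b = Φ⁻¹(0.803) = 0.853.

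**Step 4: either time accepted.** Error is 1 − Φ₂(c, c; ρ), with c = 1.960 at alpha 0.025 and c = 1.645 at alpha 0.05.

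| ρ | Power, both required (SAPS or SANS) | Error, either accepted (SAPS or SANS at 0.025) | Error, either accepted (caregiver burden, if at 0.05) |
|---|---|---|---|
| 0.5 | 69.1% | 4.5% | 8.8% |
| 0.7 | 71.7% | 4.2% | 8.0% |
| 0.9 | 75.3% | 3.5% | 6.8% |

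**Step 5: any of the four Veteran tests.** Here I use the four-variate normal, taking the correlation between different measures at different times as the product of the two correlations. The error is 8.7% at one extreme (ρ = 0.5, between measures 0.2) and 6.5% at the other (0.9 and 0.4). With one time only, the same calculation for two tests gives 4.8% and 4.7%.

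**Step 6: sample size to restore 80% with both required.** The normal approximation gives 51 per arm at ρ = 0.5 and 46 at ρ = 0.9, before the clustering allowance. (For the single test it gives 41, against 42 by noncentral t.)

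**The case against.** A reader might infer that no reading of the plan delivers both stated properties. The documents do not support that. Section 1.8 states alpha and power for a test. If months 12 and 15 are two separate claims, each test has both properties; what is then lost is control across the set of tests, which the allowance for the number of measures appears intended to protect. A fixed order, with power claimed only for the first time, would also keep both. The plan states neither arrangement. Specific Aim 1 mentions the treatment period and then the post-treatment period, but that describes timing and is not a testing order.

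A reader might also infer that the error rate is inflated as the plan stands. That too goes beyond the text. The hypotheses join the two times with 'and', and nothing says one is enough. On the literal wording error is protected and the cost is power. The inflation figures show what would follow if success at one time were later accepted.

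It is also fair to say that the size depends on assumed correlations. A high correlation shrinks the problem: at 0.9 the power loss is about 5 points. It disappears only at a correlation of 1.

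Finally, the ratio tests are only the initial analyses, and the later mixed models are described as having their own primary effect. How those models bear on the primary conclusion is a further question that this point does not settle.

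**Conclusion.** The point stands as a missing success rule with a measurable consequence. On the literal reading, power for SAPS or SANS is about 69-75% instead of above 80%, given a true ratio of 1, CV 0.3 and a between-time correlation of 0.5-0.9. Error per measure stays at or below 0.025.

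If success at either time were accepted, error would be about 3.5-4.5% per symptom measure. It would be about 6.5-8.7% for any of the four Veteran tests, against about 4.7-4.8% for two. For caregiver burden it would be about 6.8-8.8%, but only if that measure is tested at 0.05, which is inferred from the bounds, as is the split of 0.05 over SAPS and SANS.

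The effect is moderate and cheap to correct, so the plan should be changed.

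**What to change.** In Section 1.7 and in Hypotheses 1.1 and 1.2, name month 12 (end of treatment) as the primary time for SAPS, SANS and caregiver burden. Test month 15 for a measure only if month 12 is met for that measure, at the same alpha. State in Section 1.8 that the power applies to month 12 only. This keeps both stated figures with no extra subjects or visits.

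Alternatively, keep the present meaning: state that both times must pass, and restate the power for SAPS and SANS as about 69-75% under the correlation assumption above. In either case, state the alpha used for each measure, so that the basis of the 1.20 and 1.17 bounds need not be inferred.

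The cost is wording, though not in the analysis section alone. The first option changes the hypotheses under Specific Aim 1, and month 15 alone can no longer support the primary claim. The second leaves the aims intact but makes the stated power less favourable.
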